## **7.10 POSITIVE CONTROL**

The 290 µg linaclotide dose is FDA-approved for the treatment of IBS-C (Linzess®) and is included in the current trial to evaluate assay sensitivity and to provide comparative data for the patient population treated with 290 µg linaclotide within the linaclotide program. Linaclotide 290 µg will be compared to placebo utilizing the same method described for pairwise comparison described in Section 7.9.

## **7.11 SAFETY ANALYSIS**

The safety analysis will be performed using the Safety Population. The safety parameters will include AEs, clinical laboratory and vital sign parameters, and physical examination. For each of the clinical laboratory and vital sign parameters, the last non-missing safety assessment before the first dose of double-blind drug will be used as the baseline for all analyses of that safety parameter.

Continuous variables will be summarized by number of patients and mean, SD, median, minimum, and maximum values. Categorical variables will be summarized by number and percentage of patients.

### **7.11.1 Adverse Events**

Adverse events will be coded by system organ class and preferred term using the MedDRA dictionary, version 18.

An AE that occurs during the Treatment Period will be considered a treatment-emergent adverse event (TEAE) if it started after the first dose of double-blind study drug or was present prior to the date of the first dose of double-blind study drug but increased in severity after the first dose of double-blind study drug. If more than 1 AE was reported before the first dose of double-blind study drug and coded to the same preferred term, the AE with the greatest severity will be used as the benchmark for comparison with the AEs occurring during the Treatment Period. An AE that occurs more than one day after the date of the last dose of double-blind study drug will not be considered as a TEAE.

The number and percentage of patients reporting TEAEs in each treatment group will be tabulated by system organ class (SOC) and preferred term and further categorized by severity and relationship to the study drug. If a patient has more than 1 AE coded to the same preferred term, the patient will be counted only once for that preferred term using the highest severity and closest relationship to study drug for the summarization by severity and relationship to study drug, respectively.

The incidence of common ( $\geq 2\%$  of patients in any treatment group) TEAEs will be summarized by preferred term and treatment group for the Treatment Period.

A serious adverse event (SAE) that occurred between the date of the first dose of double-blind study drug and 30 days after the date of the last dose of double-blind study drug, inclusive, will be considered an on-therapy SAE. The number and percentage of patients who have on-therapy SAEs will be summarized by preferred term and treatment group. In addition, the incidence of on-therapy SAEs that led to death will be summarized separately by preferred term for each treatment group.

The number and percentage of patients in the Safety Population who have AEs leading to premature discontinuation of the study drug will be summarized by preferred term and treatment.

For patients experiencing a TEAE coded as diarrhea, the number of days from first dose of study drug for the Treatment Period to the onset date of the first occurrence of treatment-emergent diarrhea during the Treatment Period will be summarized by treatment group using descriptive

statistics. In addition, the incidence of treatment-emergent diarrhea by time of first onset for the Treatment Period will be calculated for each treatment group.

For the Screened Population, listings will be presented for patients who died, patients with SAEs, and patients with AEs leading to premature discontinuation, if any.

### **7.11.2 Clinical Laboratory Parameters**

Descriptive statistics for clinical laboratory values (in SI units) and changes from the baseline values at each assessment time point will be presented by treatment group for the following laboratory parameters:

Hematology: Absolute and differential white blood cell count, erythrocyte count, hemoglobin, hematocrit, platelet count, and red blood cell indices (mean corpuscular volume, mean corpuscular hemoglobin, and mean corpuscular hemoglobin concentration)

Chemistry: Sodium, magnesium, potassium, calcium, chloride, glucose, blood urea nitrogen, creatinine, total protein, alkaline phosphatase, albumin, total bilirubin, aspartate aminotransferase, alanine aminotransferase, bicarbonate, phosphate, and cholesterol

Clinical laboratory test values will be considered potentially clinically significant (PCS) if they meet either the lower-limit or higher-limit PCS criteria listed in [Table 3](#). The number and percentage of patients who have PCS post-baseline clinical laboratory values will be tabulated by treatment group for the Treatment Period. The percentages will be calculated relative to the number of patients with available non-PCS baseline values and at least 1 assessment in the corresponding post-baseline period. The numerator will be the total number of patients with available non-PCS baseline values and at least 1 PCS value in the corresponding post-baseline period. A supportive listing of patients with PCS post-baseline values will be provided, including the PID number, trial center, baseline and all post-baseline (including non-PCS) values. A listing of all AEs for patients with post-baseline PCS laboratory values will also be provided.

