#### 5.5.3.3 Clinical Laboratory Determinations

Blood and urine samples will be collected for clinical laboratory tests (according to the study specific manual) at the Screening Visit and other visits defined in the Schedule of Evaluations (Table 1). At the Screening Visit, the investigator will assess the clinical significance of any values outside the reference ranges provided by the central laboratory, and patients with abnormalities judged to be clinically significant will be excluded from the study.

Clinical laboratory tests will be performed according to directives in the Schedule of Evaluations (Table 1).

The following clinical laboratory tests will be performed:

- **Hematology:** Absolute and differential white blood cell count, erythrocyte count, hemoglobin, hematocrit, platelet count, and red blood cell indices (mean corpuscular volume, mean corpuscular hemoglobin, and mean corpuscular hemoglobin concentration)
- **Chemistry:** Sodium, magnesium, potassium, calcium, chloride, glucose, blood urea nitrogen, creatinine, total protein, alkaline phosphatase, albumin, total bilirubin, aspartate aminotransferase, alanine aminotransferase, bicarbonate, phosphate, and cholesterol
- **Other:** Urine drug screening (cocaine, barbiturates, amphetamines, opiates, benzodiazepine, alcohol, and cannabinoids) (screening only). Clinical significance of a positive urine drug screen will be assessed by the investigator; positive results for cocaine, barbiturates, and cannabinoids are exclusionary.
- **Pregnancy test:** Serum human chorionic gonadotropin pregnancy test (for women of childbearing potential only) should be conducted at the Screening Visit and other visits specified in the Schedule of Evaluations ([Table 1](#)). A negative urine pregnancy test must be documented at the Randomization Visit for the patient to be eligible for randomization and dosing with study drug. Positive results on the pregnancy test will exclude a patient from participating or continuing in the study.

A central laboratory will be used to evaluate all urine and blood samples (except for the urine pregnancy test), which will be collected, processed, and stored according to the instructions provided by the laboratory.

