#### 5.4.5 Clinical Laboratory Data

Fasted blood and urine samples for clinical laboratory tests will be collected at the days and times defined in the Schedule of Events (Table 2). A central laboratory will be used to evaluate all blood and urine samples (except the urine pregnancy test).

The following clinical laboratory tests will be performed:

- **Hematology:** Absolute and differential white blood cell count, erythrocyte count, hemoglobin, hematocrit, platelet count, and red blood cell indices (mean corpuscular volume, mean corpuscular hemoglobin, and mean corpuscular hemoglobin concentration)
- **Chemistry:** Sodium, magnesium, potassium, calcium, chloride, glucose, blood urea nitrogen, creatinine, total protein, alkaline phosphatase, albumin, total bilirubin, aspartate aminotransferase, alanine aminotransferase, bicarbonate, phosphate, and cholesterol
- **Other:** Urine drug screening (cocaine, barbiturates, amphetamines, opiates, benzodiazepine, alcohol, and cannabinoids) (screening only). Clinical significance of a positive urine drug screen will be assessed by the investigator; positive results for cocaine, barbiturates, and cannabinoids are exclusionary.
- **Pregnancy test:** Serum human chorionic gonadotropin pregnancy test (for women of childbearing potential only) should be conducted at the Screening Visit and other visits specified in the Schedule of Evaluations. A negative urine pregnancy test must be documented at the Randomization Visit for the patient to be eligible for randomization and dosing with study drug. Positive results on the pregnancy test will exclude a patient from participating or continuing in the study.

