**Table 3. Criteria for Potentially Clinically Significant Laboratory Results**

Parameter	SI Unit	Lower Limit	Higher Limit
CHEMISTRY			
Albumin	g/L	< 0.9 × LLN	> 1.1 × ULN
Alanine aminotransferase	U/L	—	≥ 3 × ULN
Alkaline phosphatase	U/L	—	≥ 3 × ULN
Aspartate aminotransferase	U/L	—	≥ 3 × ULN
Bicarbonate	mmol/L	< 0.9 × LLN	> 1.1 × ULN
Bilirubin, total	μmol/L	—	> 1.5 × ULN
Calcium	mmol/L	< 0.9 × LLN	> 1.1 × ULN
Chloride	mmol/L	< 0.9 × LLN	> 1.1 × ULN
Cholesterol, total	mmol/L	—	> 1.6 × ULN
Creatinine	μmol/L	—	> 1.3 × ULN
Glucose	mmol/L	< 0.8 × LLN	> 1.4 × ULN
Magnesium	mmol/L	< 0.9 × LLN	> 1.1 × ULN
Phosphate	mmol/L	< 0.9 × LLN	> 1.1 × ULN
Potassium	mmol/L	< 0.9 × LLN	> 1.1 × ULN
Protein, total	g/L	< 0.9 × LLN	> 1.1 × ULN
Sodium	mmol/L	< 0.9 × LLN	> 1.1 × ULN
Urea nitrogen	mmol/L	—	> 1.2 × ULN
Uric acid	μmol/L	< 0.9 × LLN	> 1.1 × ULN
HEMATOLOGY			
Basophils, absolute cell count	10  /L	—	> 3 × ULN
Eosinophils, absolute cell count	10  /L	—	> 3 × ULN
Hematocrit	Ratio	< 0.9 × LLN	> 1.1 × ULN
Hemoglobin	g/L	< 0.9 × LLN	> 1.1 × ULN
Lymphocytes, absolute cell count	10  /L	< 0.8 × LLN	> 1.5 × ULN
Mean corpuscular hemoglobin	pg	—	> 3 × ULN
Mean corpuscular hemoglobin concentration	g/L	—	> 3 × ULN
Mean corpuscular volume	fL	< 0.9 × LLN	> 1.1 × ULN
Monocytes, absolute cell	10  /L	—	> 3 × ULN

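### In SAP Table 3 the PCS limits for MCH and MCHC (no lower limit, upper limit above 3 × ULN) cannot in practice flag any patient, and the table has a uric acid row for an analyte that is not in the panel

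*SAP*

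**What the plan says.** Protocol Section 5.7.9.2 leaves the PCS laboratory criteria to the SAP, so SAP Table 3 is their only definition. SAP Section 7.11.2 makes Table 3 the sole route to a flag: "Clinical laboratory test values will be considered potentially clinically significant (PCS) if they meet either the lower-limit or higher-limit PCS criteria listed in" that table.

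The rows at issue, with columns for parameter, unit, lower limit and higher limit, are:

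- "Mean corpuscular hemoglobin pg — > 3 × ULN"
- "Mean corpuscular hemoglobin concentration g/L — > 3 × ULN"
- "Uric acid μmol/L < 0.9 × LLN > 1.1 × ULN"

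For comparison, the third red-cell index reads "Mean corpuscular volume fL < 0.9 × LLN > 1.1 × ULN". Hemoglobin, hematocrit and red-cell count carry the same 0.9 and 1.1 multiples.

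MCH and MCHC are measured. The hematology list in Protocol Section 5.5.3.3 includes "red blood cell indices (mean corpuscular volume, mean corpuscular hemoglobin, and mean corpuscular hemoglobin concentration", and SAP Sections 5.4.5 and 7.11.2 repeat it. The chemistry list in those same three sections ends with "aspartate aminotransferase, alanine aminotransferase, bicarbonate, phosphate, and cholesterol" and does not contain uric acid.

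**The concern.** A PCS limit is meant to pick out individual values that deserve a second look. A limit of three times ULN can do this for a cell count that can multiply. In Table 3 the same entry, with no lower limit, is used for basophils, eosinophils and monocytes. MCH and MCHC are different quantities. They are quotients (hemoglobin over red-cell count, and hemoglobin over hematocrit) that vary within a narrow band. If the upper limit is out of reach and there is no lower limit, the rule cannot fire in either direction.

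The affected outputs are the PCS counts and percentages by arm, the supportive listing of patients with PCS values, and the listing of AEs in those patients. None of them can pick up a patient on account of MCH or MCHC.

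The uric acid row is a separate and smaller matter: a criterion with no planned data behind it.

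**Working it through.** There is no stated figure in the plan to reproduce, so the check has two parts.

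**1. Can the MCH and MCHC limits be met?**

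Inputs from the documents: the Table 3 multiples. The footnote to Table 3 says that LLN and ULN come from the laboratory, and no values are given. The following reference limits are therefore assumptions:

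- MCHC ULN 340–370 g/L
- MCH ULN 32–35 pg
- hemoglobin ULN 155–175 g/L
- hematocrit LLN 0.35–0.40
- red-cell count LLN 3.8–4.5 × 10^12/L

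Thresholds:

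- MCHC: 3 × 340 = 1020 g/L to 3 × 370 = 1110 g/L, which is more than 1 kg of hemoglobin per litre of red cells.
- MCH: 3 × 32 = 96 pg to 3 × 35 = 105 pg. Since MCH = MCHC × MCV, at an MCHC of 350–400 g/L this needs a mean cell volume from 96/400 × 1000 = 240 fL to 105/350 × 1000 = 300 fL.

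Stress test. Take a patient whose hemoglobin sits at Table 3's own high limit while hematocrit or red-cell count sits at its own low limit, using the assumed values that push the quotients highest:

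- MCHC = hemoglobin / hematocrit = (1.1 × 175) / (0.9 × 0.35) = 192.5 / 0.315 = 611 g/L
- MCH = hemoglobin / red-cell count = (1.1 × 175) / (0.9 × 3.8) = 192.5 / 3.42 = 56 pg

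These are about 60% of the lowest thresholds (611/1020 = 0.60; 56/96 = 0.58). Less extreme assumptions give lower values. With hemoglobin ULN 155 and red-cell LLN 4.5, for example, MCH is 170.5 / 4.05 = 42 pg. The conclusion is the same across the assumed range. With no lower limit, a low value cannot flag either.

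**2. Does every chemistry row have a measured analyte?**

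| Source | Chemistry entries | Uric acid |
|---|---|---|
| Protocol 5.5.3.3 | 17 | no |
| SAP 5.4.5 | 17 | no |
| SAP 7.11.2 | 17 | no |
| SAP Table 3 | 18 | yes |

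The three panels are identical. Uric acid is the only Table 3 chemistry row without a panel entry, and no panel analyte lacks a row. SAP Section 8, which records changes from the protocol, does not add uric acid.

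**The case against.** The strongest reply is that little depends on these rows, and most of that reply stands.

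- SAP Section 7.11.2 still gives descriptive statistics and changes from baseline for MCH and MCHC, so a shift at group level would be reported.
- Hemoglobin, hematocrit, red-cell count and MCV have two-sided limits, so only an isolated change in MCH or MCHC goes unflagged.
- Under Protocol Section 5.5.3.1, laboratory abnormalities that are clinically significant, need intervention or are judged to be AEs by the investigator are reported as AEs, whether or not a PCS flag exists.
- The schedule has one post-baseline laboratory visit (Week 12/EOT), and the safety analysis is descriptive, with no test or decision rule.

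A reader might go further and infer that the report will print 0% for both indices in every arm, that this will pass as evidence of no abnormality, or that patients who become iron deficient will be missed. The documents do not support that. SAP Section 1 places the table and listing specifications in a separate document, so it is not known whether zero or empty rows are printed. Exclusion criterion 5 and Protocol Appendix III concern iron-deficiency anemia at entry and make no use of Table 3. On treatment, a hemoglobin below 0.9 × LLN is flagged in its own right in a patient whose baseline hemoglobin was not PCS. The match with the basophil, eosinophil and monocyte rows suggests a carried-over entry, but that is an inference and nothing here rests on it.

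The objection does not reach the rule itself. A criterion that cannot be met has no function, and the plan offers no other criterion for these two measured parameters.

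**Conclusion.** The point holds as a minor one. As Table 3 is written, MCH and MCHC cannot yield a PCS flag in any of the 8 arms, in either direction. This rests on assumed reference limits, but the gap is wide: the most extreme combination of the table's own limits reaches only about 60% of the lowest threshold. It should be read as not reachable in practice rather than strictly impossible, since a spurious hematocrit or red-cell reading could still produce such a quotient.

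The uric acid mismatch needs no assumption. It follows from comparing four intact lists and is close to clerical.

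The consequence is limited to the PCS table and its listings, where an isolated low or high MCH or MCHC would go unmarked. It does not touch efficacy, the AE tabulations or the descriptive laboratory summaries.

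**What to change.** In SAP Table 3, give MCH and MCHC attainable limits on both sides. The natural choice is < 0.9 × LLN and > 1.1 × ULN, already used for MCV, hemoglobin, hematocrit and red-cell count. On the assumed ULNs, the upper limits would be 374–407 g/L for MCHC (1.1 × 340 to 1.1 × 370) and 35.2–38.5 pg for MCH (1.1 × 32 to 1.1 × 35). The sponsor should check them against the central laboratory's ranges. Dropping the two rows from the PCS table would also cure the defect, because both indices remain in the descriptive summaries.

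Reconcile the uric acid row with the panel. Deleting the row is simplest, since all three panels agree without it. If uric acid is wanted, it must be added to the panels in both documents.

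With new limits and deletion, the cost is four cells and one row in the SAP, with no new data and no protocol change. The downside is a few more patients in the PCS listing.

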**Table 3. Criteria for Potentially Clinically Significant Laboratory Results**

Parameter	SI Unit	Lower Limit	Higher Limit
CHEMISTRY			
Albumin	g/L	< 0.9 × LLN	> 1.1 × ULN
Alanine aminotransferase	U/L	—	≥ 3 × ULN
Alkaline phosphatase	U/L	—	≥ 3 × ULN
Aspartate aminotransferase	U/L	—	≥ 3 × ULN
Bicarbonate	mmol/L	< 0.9 × LLN	> 1.1 × ULN
Bilirubin, total	μmol/L	—	> 1.5 × ULN
Calcium	mmol/L	< 0.9 × LLN	> 1.1 × ULN
Chloride	mmol/L	< 0.9 × LLN	> 1.1 × ULN
Cholesterol, total	mmol/L	—	> 1.6 × ULN
Creatinine	μmol/L	—	> 1.3 × ULN
Glucose	mmol/L	< 0.8 × LLN	> 1.4 × ULN
Magnesium	mmol/L	< 0.9 × LLN	> 1.1 × ULN
Phosphate	mmol/L	< 0.9 × LLN	> 1.1 × ULN
Potassium	mmol/L	< 0.9 × LLN	> 1.1 × ULN
Protein, total	g/L	< 0.9 × LLN	> 1.1 × ULN
Sodium	mmol/L	< 0.9 × LLN	> 1.1 × ULN
Urea nitrogen	mmol/L	—	> 1.2 × ULN
Uric acid	μmol/L	< 0.9 × LLN	> 1.1 × ULN
HEMATOLOGY			
Basophils, absolute cell count	10  /L	—	> 3 × ULN
Eosinophils, absolute cell count	10  /L	—	> 3 × ULN
Hematocrit	Ratio	< 0.9 × LLN	> 1.1 × ULN
Hemoglobin	g/L	< 0.9 × LLN	> 1.1 × ULN
Lymphocytes, absolute cell count	10  /L	< 0.8 × LLN	> 1.5 × ULN
Mean corpuscular hemoglobin	pg	—	> 3 × ULN
Mean corpuscular hemoglobin concentration	g/L	—	> 3 × ULN
Mean corpuscular volume	fL	< 0.9 × LLN	> 1.1 × ULN
Monocytes, absolute cell	10  /L	—	> 3 × ULN

**Table 3. Criteria for Potentially Clinically Significant Laboratory Results**

Parameter	SI Unit	Lower Limit	Higher Limit
count			
Neutrophils, absolute cell count	10  /L	< 0.8 × LLN	> 1.5 × ULN
Platelet count	10  /L	< 0.5 × LLN	> 1.5 × ULN
Red blood cell count	10  /L	< 0.9 × LLN	> 1.1 × ULN
White blood cell count	10  /L	< 0.7 × LLN	> 1.5 × ULN

LLN = lower limit of normal value provided by the laboratory; SI = *Le Système International d'Unités* (International System of Units); ULN = upper limit of normal value provided by the laboratory.

### 7.11.3 Vital Signs

Descriptive statistics for vital signs (systolic and diastolic blood pressures, pulse rate, respiratory rate, temperature, and weight) and changes from baseline values at each visit and at the end of study will be presented by treatment group for the Treatment Period.

Vital sign values will be considered PCS if they meet both the observed-value criteria and the change-from-baseline criteria listed in [Table 4](#). The number and percentage of patients with PCS post-baseline values will be tabulated by treatment group for the Treatment Period. The percentages will be calculated relative to the number of patients with baseline values and at least 1 post-baseline assessment for the Treatment Period. The numerator will be the total number of patients with available baseline values and at least 1 PCS post-baseline value for the Treatment Period. A supportive listing of patients with PCS post-baseline values will be provided, including the PID number, trial center, baseline and all post-baseline (including non-PCS) values.

In addition, a listing of all AEs that occurred in patients who had PCS post-baseline vital sign values will be provided.

**Table 4. Criteria for Potentially Clinically Significant Vital Signs**

Parameter	Flag	Criteria a	
		Observed Value	Change From Baseline
Sitting systolic blood pressure, mm Hg	High	≥ 180	Increase of ≥ 20
	Low	≤ 90	Decrease of ≥ 20
Sitting diastolic blood pressure, mm Hg	High	≥ 105	Increase of ≥ 15
	Low	≤ 50	Decrease of ≥ 15
Sitting pulse rate, bpm	High	≥ 120	Increase of ≥ 15
	Low	≤ 50	Decrease of ≥ 15
Weight, kg	High	—	Increase of ≥ 7%
	Low	—	Decrease of ≥ 7%

a. A post-baseline value is considered potentially clinically significant if it meets both the observed-value and the change-from-baseline criteria.

bpm = beats per minute.

#### 7.11.4 Other Safety Parameters

##### 7.11.4.1 Physical Examination

Any physical examination abnormality that the investigator considers to be potentially clinically significant and changed from the baseline will be reported as an AE. No separate analysis for Physical Examinations is planned.

#### 7.12 HEALTH OUTCOMES ANALYSIS

Health outcome analyses will be performed on the ITT population.

##### 7.12.1 Short Form-12 Health Survey Version 2

The higher-order norm-based scores, Physical Component Summary (PCS-12) and Mental Component Summary (MCS-12), will be computed at Randomization, Week 4, Week 8, and EOT. Descriptive statistics (n, mean, SD, median, minimum, and maximum) will be presented for the absolute and change-from-baseline by visit. Treatment differences for the change from baseline at each post-dose visit will be analyzed using an ANCOVA with treatment and

geographic region as fixed effects and baseline summary score as a covariate. (See Section [9.12.1](#) for scale scoring)

### **7.12.2 EuroQol-5 Dimension (EQ-5D-3L)**

Patient responses to the descriptive system (i.e., health state) will be converted to the corresponding utility score and the descriptive statistics (n, mean, SD, median, minimum and maximum) will be presented for utility score by treatment group. The same statistics will be calculated for the analog scale reflecting the patient's preference for their health state. Results will be presented at baseline and at each post-baseline week using both observed case (OC) and last observation carried forward (LOCF) approaches to missing post-baseline data. (See Section [9.12.2](#) for scale scoring)

### **7.12.3 Short Form McGill Pain Questionnaire - 2 (SF-MPQ-2)**

At each assessment of the SF-MPQ-2, total pain score and the 4 subscales (Continuous pain, Intermittent pain, Neuropathic pain, and Affective pain) will be calculated. Descriptive statistics and the change from baseline will be presented for each score. Treatment differences with respect to change from baseline will be assessed using an ANCOVA with treatment and geographic region as fixed effects and baseline value as a covariate. (See Section [9.12.3](#) for scale scoring)

